Home Rehabilitation in Patients After Primary Total Knee Arthroplasty

NCT02409719

Document Date: October 21, 2019

Date of Study Closure: January 24 2019

Statystical Analysis

Sample was calculated that 76 participants per group using media difference test with a standard deviation of 7 and an expected magnitude of difference at least five pints on the WOMAC scale with a power of β 80%, confidence 95% with statistically significant p of <=0.05 with a 20% error.

Brief Summary:

The investigators include patients attending the outpatient clinic in the area of Orthopedics and Traumatology of the investigators hospital with a diagnosis of knee osteoarthritis, which treatment requires surgery. Patients will be divided into two groups. In both groups, they will be given verbal, clear and detailed information on the approach to follow, the exercises given in brochures, and in the study group a schedule will be given in order to record rehabilitation exercises in patients after total knee replacement (TKA). Both groups will be assessed before and after surgery, together with outpatient follow-up by, WOMAC, Visual Analogue Scale and OKS (Oxford Knee Score).

Detailed Description:

Osteoarthritis (OA) is the most common rheumatic disease worldwide. OA cause joint pain and occupational disability in the adult population. In Mexico, OA is one of the top ten reasons of consultation in primary attention care.

Joint arthroplasty is a major advance in the treatment of chronic joint pain. It is indicated in patients in whose conservative medical therapy has failed. Total knee arthroplasty (TKA) is a surgery that reduces pain and improves function and quality of life in patients with knee disorders, actually is one of the most successful medical procedures. However, a critical consideration in patients with TKA is the successful control of postoperative pain. An adequate pain control allows faster rehabilitation, reduces complications and is highly correlated with patient satisfaction. A multimodal pain management decreases the use of narcotics, improve pain scores, increase patient satisfaction and allows early recovery.

Regarding postoperative rehabilitation, its suggested that rehabilitation programs are based on a biopsychosocial philosophy and integrate exercises and self-management interventions are effective in the treatment of osteoarthritis. Rehabilitation therapy an important area that should be considered. It helps people recover faster from their illness, injury or medical procedures and make possible to get back to their daily activities.

The WHO describes rehabilitation as a process that aims to enable people to maintain and achieve their physical, sensory, intellectual, functional, psychological and social level in an optimal way. It is known that rehabilitation involves contributions from various health disciplines, including physical therapy and occupational therapy and offered in inpatient, outpatient and community patients.

In patients with total knee replacement, rehabilitation interventions may involve education and exercise before surgery, early mobilization while being in the hospital and a postoperative program, along with an adequate pain management.

Perioperative care has shown an improvement in the recovery, it reduces hospital day stay, convalescent and risk of postoperative medical complications.

It has been shown that early initiation of rehabilitation within 24 hours after total knee arthroplasty reduces in-hospital time and decreases the number of sessions required to achieve autonomy, balance and normal gait. Madsen et al. demonstrated that rehabilitation exercises at home have the same effect as those made in rehabilitation group within six months postoperatively, based on a study of 80 patients randomly divided into a control- study group.

Optimal pain management is vital seeking to achieve the goal of recovery called fast track. It involves early therapy with specialized protocols, early discharge and quick recovery. Lamplot et al. demonstrated in a prospective randomized study of 36 patients, using this method, a decrease in opioid consumption and its adverse effects, a decreased pain score, a shortening time for physical therapy and an increase in patient satisfaction.

Postoperative analgesia can be achieved by a variety of techniques. These include: intravenous analgesia, epidural analgesia, techniques for peripheral nerve block and periarticular injections. All aim to control pain in patients and provide the better satisfaction.

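### The stated size of 76 per group does not follow from the stated SD, difference, power and significance level, which need 31 or 32 per group

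*Combined protocol and SAP*

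**What the plan says.** The whole justification is one sentence under the statistical analysis heading of the combined protocol and SAP. It gives:

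- the size, test and variability: "Sample was calculated that 76 participants per group using media difference test with a standard deviation of 7 and an expected magnitude of difference";
- the target: "an expected magnitude of difference at least five pints on the WOMAC scale";
- the error rates: "power of β 80%, confidence 95% with statistically significant p of <=0.05 with a 20% error".

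The Brief Summary adds the number of arms: "Patients will be divided into two groups". The sentence does not state sidedness, allocation ratio, the visit, whether the SD belongs to a score or to a change, or what the closing 20% refers to. Nowhere else does the document give a total, a loss rate or a second sample size for this trial. The header records "Date of Study Closure: January 24 2019", and the document itself is dated October 21, 2019.

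**The concern.** A two-group comparison of means is fixed by four quantities: SD, difference, power and significance level. The sentence supplies all four, so its sample size can be checked directly. A standardised difference of 5/7 = 0.71 is large, and 76 per group is far more than such an effect needs at 80% power.

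As this is the trial's only justification of its size, the disagreement leaves a reader unable to say how 76 was derived from the five points named. It is also unclear whether the plan was for 152 patients or 76, so actual enrolment cannot be judged against a reproducible target.

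**Working it through.** **Inputs.** From the sample-size sentence: SD = 7, difference = 5, power = 80%, alpha = 0.05. From the Brief Summary: two groups. Assumed, because not stated: two-sided test and 1:1 allocation.

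**Attempt to reproduce 76 per group.**

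Normal approximation:

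n per group = 2 × (z₀.₉₇₅ + z₀.₈₀)² × SD² / difference²
= 2 × (1.960 + 0.842)² × 49 / 25 = 30.77, so **31**.

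The two-sample t test gives 31.76, so **32**. One-sided, the results are 24.24 (normal) and 24.94 (t), so 25, which is further from 76.

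**If the 20% is a loss allowance** (an assumption):

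| Base n | × 1.2 | ÷ 0.8 |
|---|---|---|
| 31 | 37.2, so 38 | 38.75, so 39 |
| 32 | 38.4, so 39 | 40 |

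**Other variants.** Dividing 31 by the rank-test efficiencies 0.955 and 0.864 gives 33 to 36 per group. Allocation of 2:1 gives 24 and 48, and 3:1 gives 21 and 63. A paired or one-sample calculation gives 16 to 18. None comes near 76 per group.

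The excess is 76/32 = 2.4 to 76/31 = 2.5 times the basic requirement. With a loss allowance it is 76/40 = 1.9 to 76/38 = 2.0 times.

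**Power at the stated size** (two-sided t test, SD 7, 5 points):

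| n per group | Power |
|---|---|
| 76 | 99.2% |
| 61 (76 × 0.8 = 60.8) | 97.5% |
| 38 | 86.7% |
| 31 | 79.0% |
| 30 | 77.6% |

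**What 76 per group would fit at 80% power.** A standardised effect of 0.457, which is 3.2 points at SD 7, or 5 points at SD 10.9. If only 61 per group remain, the effect is 0.511, which is 3.6 points at SD 7, or 5 points at SD 9.8.

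**Routes that do reach 76.** Each changes something written or adds something unwritten:

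- *76 is the total.* 31 × 1.2 = 37.2, so 38 per group and 2 × 38 = 76. This needs n rounded to 31 first; unrounded, 30.77 × 1.2 = 36.9, so 37 per group and 74 in total. Dividing 31 by 0.8 gives 39 per group and 78 in total.
- *The effect was 0.50* (3.5 points at SD 7, or 5 points at SD 10; neither the 3.5 nor the 10 is in the document). n = 62.79, so 63; 63 × 1.2 = 75.6, so 76 per group. Power is then 86.5% with 76 per group and 78.2% with 61.
- *SD 7 is one of two independent components*, so the SD of the compared quantity is 7√2 = 9.9. This gives 62 per group, and 75 to 78 with a 20% allowance: near 76, not exactly 76. Power is then about 87% with 76 per group and 79% with 61.

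The arithmetic cannot choose between these routes.

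**The case against.** The strongest reply is that the closing 20% sits at the end of a list of error rates and most naturally means a type II error of 20%, which merely repeats 80% power. This is a fair reading. On it, no loss allowance is documented, and the 38 to 40 range and every route above that reaches 76 lose their basis in the text. The mismatch with 31 or 32 is then at its widest, so the reading strengthens the main point.

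Second, the 99% figure holds only if 7 is the SD of the quantity being compared. Patients are assessed before and after surgery, and the document does not tie the SD to a single score or to a change. This stands as a condition on the 99%. It does not rescue the stated size: even at SD 9.9 the requirement is 62 per group unless an allowance is added.

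Third, the candidate explanations were found by working back from 76. That is true, and none should be read as what the investigators did.

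Fourth, the consequence is small. Taken literally, the trial exceeds its own requirement, the study is closed and no analysis changes. This is also correct, and it limits the point to reporting. It does not make the sentence consistent. The wording that the difference is at least five does not help either, because a larger difference needs fewer patients.

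**Conclusion.** The concern holds. Under a two-sided 5% test with equal groups, the stated inputs need 31 or 32 per group, or 38 to 40 with an assumed 20% loss allowance. The stated 76 is about 2.4 times the first figure and about twice the second. If SD 7 applies to the compared outcome, 76 per group has about 99% power (97.5% after 20% loss) where the plan says 80%.

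Confidence is high that the figure does not follow from its inputs. There is no basis for saying which element is at fault. No reading that keeps SD 7 and 5 points shows a large loss of power: even if 76 is the total and 20% are lost, 30 or 31 per group give 78 to 79%. It should be fixed because it is the trial's sole sample-size statement and it contradicts itself, but the effect is confined to the reported figures.

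**What to change.** Recover the original calculation and restate, as one consistent set, the size (per group and total), the SD and the score or change it refers to, the difference, the power, the sidedness and the meaning of the 20%. Then, according to what is found:

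- If 76 per group, SD 7 and 5 points all stand, give the power as about 99% (97.5% if 20% are lost).
- If 76 is the total, write 38 per group and 76 in total, with about 87% power (78 to 79% if 20% are lost).
- If another difference was used, report it and its power at SD 7.
- If another SD was used, report it and its power for 5 points.

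If the calculation cannot be recovered, say so, leave the planned figure as it is, and add a dated note that 76 per group gives about 99% power under the stated inputs, taking 7 as the SD of the compared outcome. No explanation should be supplied after the fact merely because it reaches 76.

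The cost is one sentence or one dated note in the sample-size paragraph. It needs no patients, no change to recruitment and no new analysis.

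### The only method named is a two-group difference in means, although WOMAC, VAS and OKS are scored repeatedly and no primary visit or missing-data rule is stated; a mixed model on all post-operative scores would protect better against score-related loss.

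*Combined protocol and SAP*

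**What the plan says.** The section headed Statystical Analysis consists of one sentence that sizes the trial: "Sample was calculated that 76 participants per group using media difference test". Its inputs are "an expected magnitude of difference at least five pints on the WOMAC scale", "with a standard deviation of 7", "confidence 95% with statistically significant p of <=0.05" and 80% power. It ends "with a 20% error", which could mean an allowance for loss or simply the type II error.

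The Brief Summary describes the measurements: "Both groups will be assessed before and after surgery, together with outpatient follow-up by, WOMAC, Visual Analogue Scale and OKS (Oxford Knee Score". So each patient should have a pre-operative score and more than one later score on each scale. The number and dates of the visits are not given.

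Both groups receive the same information and exercise brochures. Only the study group also receives a schedule in which to record exercises.

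The document gives no primary visit, analysis model, analysis population, baseline adjustment or rule for missing scores.

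**The concern.** A difference-in-means test needs one number per patient. With no imputation rule, a patient without that number cannot contribute, even if earlier scores were recorded. The comparison is then between attenders.

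What matters is why patients are absent. If loss is random within each group, only precision suffers, even when the rates differ. If patients with poor earlier scores are more likely to be missing, and this link is stronger in one group, the remaining patients in that group look better than the group as a whole. Because only one group keeps a recording schedule, attendance could depend on progress differently in the two groups. That is a possibility; the document does not report it.

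At stake is an apparent benefit of the schedule where there is none, from a test that ignores scores the trial already collects.

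**Working it through.** **1. The plan's own figure.** Inputs from the sample-size sentence: difference 5, SD 7, power 80%, alpha 0.05 (two-sided assumed).

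- n per group = 2 × 7² × (1.960 + 0.842)² / 5² = 98 × 7.85 / 25 = 30.8, so 31.
- Allowing for 20% loss: 31/0.8 = 38.8, so 39; or 31 × 1.2 = 37.2, so 38.
- The stated 76 per group is not reproduced. It equals 2 × 38, so it may be a total, but the document does not say so.

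Taking 76 per group as written, the standard error is 7 × √(2/76) = 1.14. Power is Φ(5/1.14 − 1.96) = 99.3%. With 61 per group (20% lost) it is 97.6%. At that size, bias is a greater worry than precision.

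**2. Assumptions for the bias check.** None of these is in the document.

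- Two post-operative scores, the earlier always seen, the later one tested; SD 7 (from the plan) at both.
- Between-visit correlation r = 0.5, 0.6 or 0.8.
- No true group difference; 76 per group.
- Log-odds of missing the tested visit = logit(0.2) + k × z, where z is the standardised earlier score and a high z is a poor score.
- The slope k may differ between groups. Loss is 20% at k = 0, about 21% at k = 0.5 and about 24% at k = 1.

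**3. Formula.** Attender-only bias = 7 × r × [mean z among study attenders − mean z among control attenders]. Integrating over a standard normal z, the attender mean of z is 0 for k = 0, −0.101 for k = 0.5 and −0.204 for k = 1.

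- k = 1 in the study group, 0 in control: 7 × r × 0.204 = 0.71, 0.86 and 1.14 points.
- k = 0.5 in the study group, 0 in control: 7 × r × 0.101 = 0.35, 0.42 and 0.57 points.
- The same k in both groups: 0.

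**4. Simulation.** 4,000 trials per setting; minus favours the study group.

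| Slope, study v control | Attender-only bias (r = 0.5 / 0.6 / 0.8) | False positives |
|---|---|---|
| 1 v 0 | −0.72 / −0.85 / −1.16 | 8.2% / 10.4% / 15.0% |
| 0.5 v 0 | −0.38 / −0.43 / −0.56 | 5.1% / 6.8% / 7.2% |
| 1 v 0.5 | −0.37 / −0.39 / −0.55 | 5.6% / 6.0% / 7.2% |
| 1 v 1 | 0.00 / −0.01 / 0.01 | about 5% |

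In the 1 v 0 setting, a likelihood-type estimate that uses the earlier score has bias of about 0. Repeat runs agree within simulation error.

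**5. Precision with even random loss of 20%.** The variance ratio, attender-only to the estimate using the earlier score, is 1/(1 − 0.2 r²) = 1.05, 1.08 and 1.15. Simulation gave 1.05, 1.07 and 1.16. The variance is therefore about 5% to 14% smaller when the earlier score is used.

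**6. A different mechanism.** This run had a true difference of 5, one baseline and three later scores, loss of about 10% v 30% linked to the previous score, and r = 0.3, 0.5 and 0.7. The attender-only estimate was 5.34, 5.57 and 5.75; using earlier scores it was 5.00, 5.01 and 4.97. With about 20% loss in each group by the same mechanism, the attender-only estimate was 4.97, 5.02 and 5.01.

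**The case against.** The strongest reply is that the plan never says it will run this test at one visit on attenders. The test is named only to size the trial, and a two-means formula is routinely used to size trials that are analysed in other ways. That stands. A reader might infer that a single-visit, attender-only analysis is prescribed, but the document fixes neither the visit nor the treatment of absentees. The point is therefore conditional on the test being applied as named. If another analysis was intended, it still has to be written down.

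A reader might also infer that uneven loss is itself a source of bias. It is not: loss must relate to outcome, and differently in the two groups.

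The largest figures come from an extreme case, with score-related loss in the study group only and none in control. That stands too: the bias roughly halves at slope 0.5 v 0 and vanishes when the mechanism is shared. With slope 1 v 0 but a base loss rate of 10%, false positives are 6.2%, 7.3% and 8.5%. Treating the earlier score as always seen also favours the repeated-measures analysis. Nothing in the document shows that patients who stop recording miss clinic, or that any such loss occurred.

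Finally, the mixed model has limits. It assumes that loss is explained by observed scores, and its gain depends on a number of post-operative scores that is not given. The study closed on January 24, 2019, before the document date of October 21, 2019. These points call for a sensitivity analysis and a label on timing. They do not favour the attender-only test, which needs a stronger assumption.

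**Conclusion.** The point holds in conditional form. The plan collects repeated scores, names only a test that uses one value per patient, and states no primary visit or missing-data rule.

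If the test is applied as named, the bias under the assumed loss of about 20% runs from 0 to about 1.2 WOMAC points. The upper figure is 1.16/5 = 23% of the five-point target, with a 15% false-positive rate against a nominal 5%; it is the top of an assumed range, not an expected value. The range rests on the stated SD of 7 and 76 per group, and on assumed loss rates, mechanisms and correlations.

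A reader might conclude that the trial's result is biased. The document does not support that, since it reports no loss and no final analysis. Nor is lost power the reason to act, given 99.3% at 76 per group. The reason is that a safer analysis can be had from data the trial already collects.

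**What to change.** Specify the WOMAC analysis as one mixed model for repeated measures on all post-operative scores:

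- Terms: group, visit, group-by-visit, the pre-operative score and its interaction with visit; unstructured covariance.
- Population: every allocated patient with at least one post-operative score, in the assigned group.
- Result: the between-group contrast with its 95% CI at one named primary visit.
- VAS and OKS: the same model.
- Missing data: counts of missing scores by group and visit, including patients with no post-operative score, and a simple sensitivity analysis for loss not explained by observed scores (for example, shifting the unobserved study-group scores by a range of fixed amounts).
- Timing: label the model post hoc unless it is shown to have been fixed before the data were seen.

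The cost is wording and slightly more programming; no new data are needed. The downside is reliance on missing at random, which is a weaker assumption than an attender-only test requires.

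### No use is stated for the pre-surgery WOMAC, VAS and OKS scores; if the mean-difference test in the sample-size sentence is the analysis and allocation was random, baseline-adjusted ANCOVA would in large samples be at least as precise

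*Combined protocol and SAP*

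**What the plan says.** The section headed Statystical Analysis is a single sample-size sentence. It reads "Sample was calculated that 76 participants per group", "using media difference test with a standard deviation of 7", and it targets "an expected magnitude of difference at least five pints on the WOMAC scale" with 80% power at a 0.05 significance level. It does not say whether the test would be applied to follow-up scores or to before-after changes, or whether 7 is the SD of a score or of a change.

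The Brief Summary gives the measurements: "Both groups will be assessed before and after surgery, together with outpatient follow-up by, WOMAC, Visual Analogue Scale and OKS (Oxford Knee Score". No model, covariate, definition of change or primary time point appears anywhere in the document.

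On allocation, the Brief Summary says "Patients will be divided into two groups". Randomisation into two groups is described in the Detailed Description for a cited trial ("study of 80 patients randomly divided into a control- study group"), but not for this trial's own patients.

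The header gives "Document Date: October 21, 2019" and "Date of Study Closure: January 24 2019".

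**The concern.** A pre-surgery score on the same scale usually carries some information about the follow-up score. A two-group test on follow-up scores ignores it. A test on changes uses it with a fixed weight of one, which is generally not the best weight. ANCOVA estimates the weight from the data.

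If the mean-difference test is what was run, the confidence interval for the group difference would be as wide as, or wider than, the planned measurements allow. Under random allocation, ANCOVA also removes the effect of chance imbalance in the baseline score; that is the same gain in precision seen from another side, not a second benefit. What is at stake is interval width, not the validity of the comparison.

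**Working it through.** **Inputs from the document:** 76 per group, SD 7, difference 5 WOMAC points, 80% power, significance level 0.05 (taken as two-sided).

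**Assumptions not in the document:** 7 is the SD of the follow-up score; the correlation ρ between baseline and follow-up is 0.3 to 0.6; allocation is random. The baseline SD is k times the follow-up SD.

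**1. The plan's own figure.** n per group = 2 × [7 × (1.960 + 0.842) / 5]² = 30.8, so 31. Reading the 20% error as a loss allowance gives 31/0.8 = 38.75, so 39, or 31 × 1.2 = 37.2, so 38. None of these is 76. A two-arm total of 38 + 38 is 76, which suggests, but does not prove, that a total was labelled as per group. The absolute widths below take 76 per group literally; the percentage gains do not depend on it.

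**2. Large-sample variance factors, random allocation**
- Follow-up scores: 1
- Changes: 1 + k² − 2ρk
- ANCOVA: 1 − ρ²

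ANCOVA's advantage is ρ² over follow-up scores and (k − ρ)² over changes. Neither can be negative, and neither result needs equal SDs.

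**3. Half-widths at 76 per group.** SE = 7 × √(2/76) = 1.136, and 1.96 × 1.136 = 2.23 points for follow-up scores. With equal SDs (k = 1):

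| ρ | Follow-up scores | Changes: 2.226 × √(2 − 2ρ) | ANCOVA: 2.226 × √(1 − ρ²) |
|---|---|---|---|
| 0 | 2.23 | 3.15 | 2.23 |
| 0.1 | 2.23 | 2.99 | 2.21 |
| 0.2 | 2.23 | 2.82 | 2.18 |
| 0.3 | 2.23 | 2.63 | 2.12 |
| 0.5 | 2.23 | 2.23 | 1.93 |
| 0.6 | 2.23 | 1.99 | 1.78 |

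For ρ from 0.3 to 0.6, ANCOVA is 0.10 to 0.45 points narrower than follow-up scores. As a proportion, 1 − √0.91 is about 5% and 1 − √0.64 is 20%. It would match the follow-up-score precision with 76 × (1 − ρ²), or about 69 to 49 per group.

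**4. Unequal SDs.** For k from 0.75 to 1.5 and the same ρ, changes range from 1.81 to 3.41 while ANCOVA stays at 2.12 to 1.78. At k = 0.75 and ρ = 0.6 the gain over changes is only 1.81 − 1.78 = 0.03 points. Simulation with 20,000 trials per setting agreed with these values to within about 0.03 points.

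**5. If 7 is instead the SD of changes (equal SDs).** Changes give 2.23, and ANCOVA gives 2.226 × √((1 + ρ)/2) = 1.79 to 1.99.

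**6. Small-sample cost.** Estimating the slope multiplies ANCOVA's variance by about 1 + 1/148 at 76 per group. With t quantiles, ANCOVA at ρ = 0 is 2.251 against 2.244, about 0.01 points wider. Break-even is near ρ = 0.08 (near 0.12 at 38 per group).

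**7. If the groups differ at baseline by d baseline SDs.** With equal group sizes, ANCOVA's variance is multiplied by about 1 + d²/4. At d = 1 and ρ = 0.3, 2.226 × √(0.91 × 1.25) = 2.37, wider than 2.23. Break-even ρ is about 0.24 at d = 0.5 and 0.45 at d = 1. These imbalances are illustrations; the document reports none.

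**8. Power for 5 points, unadjusted follow-up scores.** At 76 per group it is about 99% (99.2% from the t distribution). At 38 per group it is about 87%, with a half-width of 3.15 against 3.00 to 2.52 for ANCOVA at ρ from 0.3 to 0.6.

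**The case against.** The strongest objection is that the document never says the sample-size test is the final analysis. This stands: what is documented is an unspecified analysis, not a demonstrably inefficient one. A reader might infer that the sponsor chose to discard the baseline scores, but the text is silent on their use and does not support that. The point therefore has to stay conditional.

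Second, random allocation is not stated. This also stands, and it limits the precision claim as well as any claim about bias. A reader might infer that ANCOVA is always at least as precise, or that it would repair a comparison of non-randomised groups. Neither follows: a systematic imbalance can make ANCOVA's interval wider, and then neither ANCOVA nor change scores is guaranteed unbiased. No bias figure is claimed.

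Third, the correlation and the SD ratio are assumed, so the documents cannot show whether the gain is worth having. That is correct, and it is why a range reaching down to zero correlation is shown.

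Fourth, under randomisation an unadjusted comparison is valid, and a repeated-measures model would be another acceptable use of the data. Both are true. ANCOVA at one time point is simply the smallest change.

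Fifth, the study had closed before the document was dated, so an adjusted analysis may only be supplementary. This stands and shapes the fix.

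What survives is that the baseline scores are already planned and, under random allocation, adjusting for them costs at most about 0.01 points of half-width at 76 per group.

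**Conclusion.** The point holds as a minor, conditional recommendation. Two facts come directly from the document: one comparison is named, in the sample-size sentence, and no use is given for the pre-surgery scores. The precision statement rests on three further conditions: that this test is the analysis, that allocation was random, and that the sample is large enough for the slope-estimation cost to be negligible.

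The relative gain over follow-up scores depends only on ρ, so the same percentages would apply to VAS and OKS at the same ρ, although no SD is given for either.

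A reader might infer from the power of about 99% that precision hardly matters, or from the wider intervals that the trial is underpowered. The documents support neither firmly. The 99% takes 76 per group literally, a figure the stated inputs do not reproduce; at 38 per group, precision would matter more. No conclusion of the trial is shown to change.

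**What to change.** For each of WOMAC, VAS and OKS, analyse the follow-up score at a named time point by ANCOVA on group plus that scale's own pre-surgery score. Report the adjusted difference with its 95% CI alongside the unadjusted mean difference. State how the two groups were formed, and say that adjustment does not replace randomisation.

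State when the adjusted analysis was specified. If that was after the data were seen, label it post hoc and present it as supplementary to the mean-difference test.

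The cost is a short paragraph in the analysis section and one regression per scale. No new data are needed, since the pre-surgery assessments are already part of the plan.
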